6.6 Monitoring Subject Compliance

Black raspberries will be dispensed only to eligible patients under the supervision of the investigator or identified subinvestigator(s). The appropriate study personnel will maintain records of product receipt and dispensing. The patient will complete a drug diary to ensure compliance.

The patient will be seen every cycle by a healthcare professional or study staff for compliance. Patients will also be required to complete a food diary at home while taking BRBs and instructed to return the diary to clinic for assessment every cycle.

6.7 Follow-Up Period

Patients removed from the study treatment for unacceptable SAEs will be followed until resolution or stabilization of the adverse event.

7 ADVERSE EVENTS: DEFINITIONS AND REPORTING REQUIREMENTS

7.1 Defining and reporting an Adverse Event

Definition. Any clinically relevant deterioration in laboratory assessments or other clinical finding is considered an AE.

Prior to the trial. Planned hospital admissions or surgical procedures for an illness or disease that existed before the patient was enrolled in the trial are not to be considered AEs unless the condition deteriorated in an unexpected manner during the trial (e.g. surgery was performed earlier or later than planned).

Reporting source. AEs may be spontaneously reported by the patient and/or in response to an open question from study personnel or revealed by observation, physical examination or other diagnostic procedures.

For non-serious AEs, the investigator must determine both the intensity of the event and the relationship of the event to study drug administration.

Signs or symptoms reported as adverse events will be graded and recorded by the investigator, according to the CTCAE version 4. When possible, signs and symptoms indicating a common underlying pathology should be noted as one comprehensive event.

Follow-up of Adverse Events

All adverse events will be followed with appropriate medical management from the first dose of BRBs until 30 days following the last dose of treatment.

The investigator and his or her team will follow the Medical College of Wisconsin policies related to adverse event reporting.

7.2 Defining and reporting a Serious Adverse Event (SAE)

Serious Adverse Event (SAE) means any untoward medical occurrence that at any dose:

- **Death.** Results in death.
- Life threatening. Is life threatening (refers to an AE in which the patient was at risk of death at the time of the event. It does not refer to an event which hypothetically might have caused death if it were more severe).
- **Hospitalization**. Requires inpatient hospitalization or prolongation of an existing hospitalization (excluding planned hospitalization).
- **Disability/incapacity**. Results in persistent or significant disability or incapacity. (Disability is defined as a substantial disruption of a person's ability to conduct normal life functions).
- **Medically important event**. This refers to an AE that may not result in death, be immediately life threatening, or require hospitalization, but may be considered serious when, based on appropriate medical judgment, may jeopardize the patient, require medical or surgical intervention to prevent one of the outcomes listed above, or involves suspected transmission via a medicinal product of an infectious agent. Examples of such medical events include allergic bronchospasm requiring intensive treatment in an emergency room or at home, blood dyscrasias or convulsions that do not result in inpatient hospitalization, or the development of drug dependency or drug abuse; any organism, virus, or infectious particle (e.g., prion protein transmitting Transmissible
- Spongiform Encephalopathy), pathogenic or nonpathogenic, is considered an infectious agent.

Clarification should be made between a serious AE (SAE) and an AE that is considered severe in intensity (Grade 3 or 4), because the terms serious and severe are NOT synonymous. The general term severe is often used to describe the intensity (severity) of a specific event; the event itself, however, may be of relatively minor medical significance (such as a Grade 3 headache). This is NOT the same as serious, which is based on patient/event outcome or action criteria described above, and is usually associated with events that pose a threat to a patient's life or ability to function. A severe AE (Grade 3 or 4) does not necessarily need to be considered serious. For example, a white blood cell count of 1000/mm3 to less than 2000 is considered Grade 3 (severe) but may not be considered serious. Seriousness (not intensity) serves as a guide for defining regulatory reporting obligations.

Reporting SAEs

Serious AEs must be reported from the first dose of BRBs through 30 days after completion of study treatment or until they are resolved or are clearly determined to be due to a patient's stable or chronic condition or intercurrent illness(es).

For serious AEs, the investigator must determine both the intensity of the event and the relationship of the event to study drug administration.

Since this is an investigator-initiated study, the principal investigator, also referred to as the sponsor-investigator, is responsible for reporting serious adverse events (SAEs) to any regulatory agency and to the sponsor-investigator's IRB when required.

AEs which are serious must be reported to the Data Safety Monitoring Committee (DSMC) from the first dose of BRBs through 30 days after completion of treatment on the study.

Reporting to the Data and Safety Monitoring Committee

Regardless of expectedness or causality, all SAEs must also be reported to the DSMC as soon as possible, but no later than five calendar days of the sponsor-investigator's observation or awareness of the event.

Report Method: The investigator will use email to report SAEs to the DSMC. The SAE report must include event term(s), serious criteria, and the sponsor-investigator's or sub-investigator's determination of both the intensity of the event(s) and the relationship of the event(s) to study drug administration. Intensity for each SAE, including any lab abnormalities, will be determined by using the NCI CTCAE version 4 as a guideline whenever possible.

The criteria are available online at http://ctep.cancer.gov/reporting/ctc.html.

7.3 Unanticipated Problem Involving Risk to Subject or Other (UPIRSO)

The investigator and his or her team will follow the Medical College of Wisconsin policies related to unanticipated problems involving risks to subjects or others. This information may be found on the Human Research Protection Program website.

7.4 Procedure for Reporting Drug Exposure during Pregnancy and Birth Events

If a woman becomes pregnant, or suspects that she is pregnant, while participating in this study, she must inform the investigator immediately and permanently discontinue the study drug. The sponsor-investigator must notify the DSMC by email. The pregnancy must be followed for the final pregnancy outcome.

If a female partner of a male patient becomes pregnant during the male patient's participation in this study, the sponsor-investigator must also immediately notify the DSMC. Every effort should be made to follow the pregnancy for the final pregnancy outcome.

Suggested Pregnancy Reporting Form:

• Pregnancy Report Form (a sample is provided in Appendix 7)

7.5 Common AE List

In a previous pilot study, healthy subjects consumed 45 g of freeze-dried berries for 14 days and the berries were well tolerated.

However, side effects are always a possibility and patients will be asked to report any change in their health status or potential adverse events

Expedited Reporting to the Food and Drug Administration

If the study is being conducted under an IND, the sponsor-investigator is responsible for determining whether or not the suspected adverse reaction meets the criteria for expedited reporting in accordance with Federal Regulations (21 CFR §312.32).

The investigator must report in an IND safety report any suspected adverse reaction that is both serious and unexpected. The sponsor-investigator needs to ensure that the event meets all three definitions:

- Suspected adverse reaction
- Unexpected
- Serious

If the adverse event does not meet all three of the definitions, it should not be submitted as an expedited IND safety report.

The timeline for submitting an IND safety report to FDA is no later than **15 calendar days** after the investigator determines that the suspected adverse reaction qualifies for reporting (21 CFR 312.32(c)(1)).

Any unexpected fatal or life-threatening suspected adverse reaction will be reported to FDA no later than seven calendar days after the investigator's initial receipt of the information (21 CFR 312.32(c)(2)).

Any relevant additional information that pertains to a previously submitted IND safety report will be submitted to FDA as a Follow-up IND Safety Report without delay, as soon as the information is available (21 CFR 312.32(d)(2)).

Suggested Reporting Form:

 US FDA MedWatch 3500A: http://www.fda.gov/Safety/MedWatch/HowToReport/DownloadForms/default.htm

Any other form deemed appropriate by the sponsor-investigator.

8 PHARMACEUTICAL INFORMATION

8.1 Black Raspberries

Product Description

The freeze-dried black raspberry powder is available from BerriProducts, Inc. in 25-gram dosing packets. Each bag contains around 500 freeze-dried black raspberries.

Black raspberries for this powder are grown, harvested mechanically when ripe, washed immediately after harvest and frozen at -20°C.

They are freeze dried under Good Manufacturing Practice (GMP) conditions by Oregon Freeze Dry in Albany, Oregon, the largest U.S. freeze-drying company. After freeze drying, the berries are ground into a powder, and the powder is tested for contamination with fungi, e. coli, salmonella and listeria. In addition, the content of 26 different nutrients are measured in the powder on a routine basis, as described by Stoner. (19)

Classification:

Phytomedicine.

Mechanism of Action:

Their modes of action include inhibition of carcinogen activation and stimulation of carcinogen detoxification. In addition, they reduce the binding of the reactive metabolites of carcinogens to DNA, downregulate genes associated with cancer development, upregulate of genes involved in cell-cycle control and stimulate apoptosis and inhibit angiogenesis.

Metabolism:

Anthocyanins are excreted in intact forms and metabolized into methylated derivatives in human urine. The urinary excretion of anthocyanins reaches maximum concentration during the four- to eight-hour period after black raspberry ingestion.

Contraindications:

Allergic reaction to BRBs

Side Effects:

As noted, side effects are a possibility and potential adverse events (i.e., headache, dizziness, nausea, vomiting, diarrhea, cramping) will be monitored.

Solution Preparation/ Investigational Agent Administration

Twenty-five grams of freeze-dried BRBs will be mixed in 8 ounces of water and consumed twice daily at least six hours a part. If patient is unable to tolerate the taste, he or she may mix the BRB with milk, ice cream or a smoothie.

Storage Requirements

Black raspberries will be stored in Investigational Drug Pharmacy in a freezer at minus 20 degrees Celsius and transported to the clinic in a cooler with an ice pack. Patients need to store BRBs in the freezer at home.

Stability

Freeze-dried products have the same size and shape as the original frozen material and have excellent stability and convenient reconstitution when placed in water.

Route of Administration

Oral administration.

Nursing Implications

Dispensing: Patients will receive oral black raspberries while receiving their supportive care. At office visits, patients will pick up black raspberry doses for the next cycle.

Compliance: Clinical staff will collect phenolic-rich food diaries from patients which reflect the previous cycle.

Handling

No special handling instructions.

Availability

The supplier is BerriProducts, Inc.

Agent Ordering

MCW will obtain black raspberry powder directly from BerriProducts, Inc. in Corvallis, Oregon as study supply.

Contact information: BerriProducts, Inc., [name]. [contact].

Agent Accountability

The investigator, or a responsible party designated by the investigator, must maintain a careful record of the inventory and disposition of black raspberries.

9 REPORTING AND DOCUMENTING RESULTS (MEASUREMENT OF EFFECT)

9.1 Evaluation of Efficacy (or Activity) Definitions

Evaluable for toxicity: All patients will be evaluable for toxicity from the time of their first study drug treatment.

Evaluable for response: Only patients who have undergone at least three cycles of treatment are evaluable for response.

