1 BACKGROUND

Myelodysplastic Syndromes (MDS)

Myelodysplastic syndromes (MDS) are a group of bone marrow disorders characterized by progressive cytopenias and progression to acute myeloid leukemia (AML). (1) Each year, an estimated 10,000 new patients with MDS above the age of 65 are diagnosed. (2) Clinicians use the French-American-British (FAB) and the World Health Organization (WHO) systems, in addition to the International Prognostic Scoring System (IPSS), to classify MDS. (3) The latter is the most commonly used prognostic scoring system, and it includes the percentage of blasts/morphology, number of cytopenias and cytogenetic abnormalities. The IPSS system divides patients into four prognostic groups — low, intermediate-1, intermediate-2 and high-risk disease. The median survival is 4.8, 2.7, 1.1 and 0.5 years for patients >60 years old with low, intermediate-1, intermediate-2 and high-risk disease, respectively. The median age at diagnosis for patients with MDS is 76 years and 86% of patients are above the age of 65. (2) As most patients with MDS are older, therapy with a low toxicity would be desirable for this patient population.

Current therapy for MDS

Hematopoietic stem cell transplantation (HSCT) remains the only cure for MDS. Clinicians also have other therapy options that correspond with disease risk in treating MDS. For example, supportive care, which may consist of transfusions and growth factors therapy, remains the backbone of low-risk MDS treatment. (4) 5q- syndrome patients are treated with antithymocyte globulin therapy and lenalidomide. (5) Azacitidine or decitabine (6,7) are first-line therapies for high-risk disease patients who can tolerate them. Azacitidine, decitabine, and lenalidomide are FDA-approved therapies for MDS treatment. The first two drugs are hypomethylating agents (HMAs). HMAs have yielded a response rate ranging from 30–50% for an average of 12 months in MDS patients.

Treatment of MDS or MDS/MPN with Hypomethylating Agents

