4.1 Inclusion Criteria

A potential subject must meet all the following inclusion criteria to be eligible to participate in the study.

1. Patients must have a confirmed diagnosis of myelodysplastic syndrome or myelodysplastic syndrome/ myeloproliferative neoplasms (MDS/MPN) proven by bone marrow biopsy/aspirate.

- 2. Patients with cytopenias (blood cell counts lower than the institutional lower limit of normal within the eight weeks prior to the study) who are receiving or received:
 - red blood cell transfusions
 - observation
 - platelet transfusions
 - erythropoietin
 - granulocyte colony-stimulating factors
 - granulocyte-macrophage colony-stimulating factors
 - hydrea
- 3. Age >18 years.
- 4. Predicted life expectancy of at least 12 weeks.
- 5. Patients should be expected to stay on the same therapy for the period of the study.
- 6. Patients who do not have an indication for and/or are believed to be unable to tolerate a hypomethylating agent are eligible for the study.
- 7. Reproductive requirements:

Female patients must meet one of the following:

- Postmenopausal for at least one year before the screening visit, or
- Surgically sterile, or
- If they are of childbearing potential, agree to practice two effective methods of contraception from the time of signing of the informed consent form through 30 days after the last dose of study drug, AND
- Must also adhere to the guidelines of any treatment-specific pregnancy prevention program, if applicable, or
- Agree to practice true abstinence when this is in line with the preferred and usual lifestyle of the subject. (Periodic abstinence [e.g., calendar, ovulation, symptothermal, postovulation methods] and withdrawal are not acceptable contraception methods.)

Male patients, even if surgically sterilized (i.e., status postvasectomy), must agree to one of the following:

- Practice effective barrier contraception during the entire study treatment period and through 30 days after the last study drug dose, OR
- Must also adhere to the guidelines of any treatment-specific pregnancy prevention program, if applicable, OR
- Agree to practice true abstinence when this is in line with the preferred and usual lifestyle of the subject. (Periodic abstinence [e.g., calendar, ovulation, symptothermal, postovulation methods] and withdrawal are not acceptable methods of contraception.)
- 8. Ability to understand a written informed consent document, and the willingness to signit.

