5.6 Study Withdrawal Procedures

Patients may continue treatment for one year from the time of study entry.

In the absence of treatment delays due to adverse events, treatment may continue until:

- Disease progression, as defined by the modified IWG criteria (Appendix 2)
- General or specific changes in the patient's condition render the patient unacceptable for further treatment in the investigator's judgment.
- Intercurrent illness that prevents further treatment administration
- Patient decides to withdraw from the study
- Significant patient noncompliance with protocol
- Unacceptable adverse event(s) per PI discretion

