9.4 Response Criteria

The patient's best clinical response will be assessed, based on the modified IWG response criteria (Appendix 2) while receiving BRBs.

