10 STATISTICAL CONSIDERATIONS

Methods for berry components (ellagic acid and anthocyanins)

A descriptive analysis will be performed for ellagic acid and anthocyanin data. Means, medians and confidence intervals will be calculated for all absolute and relative differences.

Methods for analysis of methylation changes

The primary analysis will consist of six mixed effect models with a random effect for patient, and 4 pairwise comparison of baseline methylation to each treatment times. A Bonferroni correction for 24 total comparisons will be applied to maintain a 5% experimentwise error rate. The primary outcome will be analyzed as the relative methylation rate (difference/baseline). Absolute methylation will also be analyzed, if appropriate for this data. Missing data will be assumed to be missing at random (MAR). Patients with partial data before six6 cycles, e.g., from their visits at cycle 2 or 3, will be included in the analysis.

Power calculation

Strong changes in methylation levels have been observed in pilot data, with mean differences exceeding 20% difference, with standard deviations ranging from six to eight. This study calls for comparing the methylation differences from baseline to each treatment time points, and repeated over six different genes of interest, for a total of 24 comparisons. Based on a two-sided paired *t*-test with 5% type I error rate with Bonferroni adjustment for 24 comparisons, a standard deviation of 8.0 and methylation difference of 12%, a sample size of 16 will be sufficient for 95% power. To date, seven patients were enrolled to the trial and they all finished three cycles of BRB treatment. Based on the current compliance to the treatment protocol, no one dropped and no one was noncompliant. Therefore, we assume that there will be no more than 5% non-compliance to the treatment protocol. An addition of 5% will be recruited, so power can be maintained using nonparametric methods (Wilcoxon Signed-Rank test). Therefore, this brings the final sample required sample size to 18 patients to maintain the power of the study. *Toxicity monitoring plan (stopping rule)*

Severe toxicity is not expected with BRB. As a precaution for unexpected high toxicity, the trial enrolment will be pause and the protocol reviewed if a toxicity rate exceeding 15% is observed. The following table gives the stopping rule a Pocock-type boundary for 15% toxicity rate:

# enrolled	3	5	9	12	16	18
Pause if toxicities	3	4	5	6	7	8

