APPENDIX 2. MODIFIED IWG RESPONSE CRITERIA

Hematologic	Response Criteria (responses must last at least 8 weeks)				
Improvement (HI)					
Erythroid response	- Hgb increase by ≥ 1.5 g/dL.				
(pretreatment, < 11 a/dL)	- Relevant reduction of RBC transfusion units by an absolute				
. ,	number of at least 4 RBC transfusions/8 wk compared with				
	the pretreatment transfusion number in the previous 8 wk.				
	- Only RBC transfusions given for an Hgb of \leq 9.0 g/dL				
	pretreatment will count in the RBC transfusion response				
	evaluation.				
Platelet response	- Absolute increase of \geq 30 x 109/L for patients starting with				
(pretreatment, < 100 x 109/L)	> 20 x 109/L platelet.				
	- Increase from < 20 x 109/L to > 20 x 109/L and by at least				
	100%.				
Neutrophil	At least 100% increase and an absolute increase > 0.5 x 109/L.				
response (pretreatment					
< 1.0 x 109/L)					
Progression or	At least one of the following:				
relapse after HI	- At least 50% decrement from maximum response levels in				
	aranulocytes or platelets				
	= Reduction in Hab by > 1.5 a/dl				
	- Reduction in rigb by ≥ 1.5 g/dE.				
	- i ransiusion dependence in transfusion independent				
	patients.				

Category	Response criteria (responses must last at least 4 weeks)
Complete remission	Bone marrow: ≤ 5% myeloblasts with normal maturation of all cell lines Persistent dysplasia will be noted
	Peripheral blood: Hgb \geq 11 g/dL Platelets \geq 100 × 10 ⁹ /L Neutrophils \geq 1.0 × 10 ⁹ /L Blasts 0%
Partial remission	All CR criteria if abnormal before treatment except: Bone marrow blasts decreased by ≥ 50% over pretreatment but still > 5% Cellularity and morphology not relevant
Marrow CR	Bone marrow: $\leq 5\%$ myeloblasts and decrease by $\geq 50\%$ over pretreatment
	Peripheral blood: if HI responses, they will be noted in addition to marrow CR
Stable disease	Failure to achieve at least PR, but no evidence of progression for > 8 weeks.
Failure	Death during treatment or disease progression characterized by worsening of cytopenias, increase in percentage of bone marrow blasts, or progression to a more advanced MDS FAB subtype than pretreatment
Cytogenetic response	Complete: Disappearance of the chromosomal abnormality without appearance of new ones Partial: At least 50% reduction of the chromosomal abnormality

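### The three-cycle rule in Section 9.1 leaves out of the response set patients who die or stop for progression before completing three cycles, although Appendix 2 scores them as Failure; the upward effect on a response proportion is modest

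*Combined protocol and SAP*

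**What the plan says.** Section 9.1 uses two sets. Toxicity covers every patient from the first dose. For response: "Only patients who have undergone at least three cycles of treatment are evaluable for response". A cycle is 28 days.

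Appendix 2 defines Failure as "Death during treatment or disease progression characterized by worsening of cytopenias", among other signs of progression, and attaches no minimum number of cycles. Section 5.6 lists progression by the Appendix 2 criteria among the reasons treatment ends, in whatever cycle it occurs.

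Response is a secondary endpoint (Section 3.4). Section 9.4 says: "The patient's best clinical response will be assessed, based on the modified IWG response criteria (Appendix 2) while receiving BRBs". Formal response assessments fall on day 1 of cycles 4 and 7 and at the follow-up visit (Study Calendar, Sections 3.1, 5.4 and 5.5).

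Section 10 covers berry components, methylation, power and toxicity monitoring. It has no response analysis, no response denominator and no missing-data rule for response. Its sentence on partial data, under which patients with data only "from their visits at cycle 2 or 3, will be included in the analysis", stands under the methylation heading.

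**The concern.** Membership of the response set depends partly on the outcome. Death or progression can itself stop a patient short of three cycles, and the same event is what Appendix 2 calls Failure. No other section returns these patients to the response set. If the set serves as the denominator, known failures drop out while patients who do well stay in, so the response proportion can only rise, provided those who leave early are non-responders.

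Some early loss is possible. Section 4.1 asks for "Predicted life expectancy of at least 12 weeks", which equals the three-cycle window (12 x 7 = 84 = 3 x 28 days), and it sets no ceiling on disease risk. What is at stake is the estimate of clinical activity in a single-group study of 18 patients, where each omitted failure shifts the figure.

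**Working it through.** **1. The plan's own figure.** The documents give no response rate, target or power for response. The only relevant number is the sample size of 18, which comes from the methylation calculation. A two-sided paired t-test at 0.05/24 with difference 12 and SD 8.0 has power 0.957 at n=15 and 0.974 at n=16, so 16 does suffice for 95%. Two 5% allowances give 16 x 1.05 x 1.05 = 17.64, or 16/0.95/0.95 = 17.7, hence 18. The figure reproduces, and 18 is used below as the all-treated denominator.

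**2. Who is lost.**

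| Patient | Appendix 2 outcome | In the Section 9.1 set? |
|---|---|---|
| Dies before completing three cycles | Failure | No |
| Stops for progression before completing three cycles | Failure | No |
| Completes three cycles, found progressed at C4D1 | Failure | Yes |
| Stops early for another reason, no response documented | Not defined as Failure | No |

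**3. Size of the inflation.** Let r be the responders (all in the Section 9.1 set) and k the non-responders who leave before three cycles. The Section 9.1 proportion is r/(18-k), the all-treated proportion is r/18, and their ratio is 18/(18-k): 1.059 at k=1, 1.125 at k=2 and 1.286 at k=4. Neither r nor k is in the documents; the values below are assumptions. Intervals are exact (Clopper-Pearson) 95%.

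| k | r=4 | r=2 | r=0 |
|---|---|---|---|
| 0 | 4/18 = 22.2% (6.4-47.6) | 11.1% | 0% |
| 1 | 4/17 = 23.5% (6.8-49.9) | 11.8% | 0% |
| 2 | 4/16 = 25.0% (7.3-52.4) | 12.5% | 0% |
| 4 | 4/14 = 28.6% (8.4-58.1) | 14.3% | 0% |

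**4. How large k might be.** Section 10 reports that "seven patients were enrolled to the trial and they all finished three cycles of BRB treatment", so k is 0 so far and 18 - 7 = 11 patients remain. Section 1 states: "The median survival is 4.8, 2.7, 1.1 and 0.5 years for patients >60 years old", for low, intermediate-1, intermediate-2 and high risk in turn. Assume a constant death hazard from first dose, all 11 patients in one risk group, and progression not counted. Then the 84-day death risk is 1 - 0.5^(0.230/median), because 84 days = 0.230 years.

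| Risk group | Median (years) | 84-day death risk | Expected deaths in 11 | P(4 or more) |
|---|---|---|---|---|
| Low | 4.8 | 3.3% | 0.4 | 0.03% |
| Intermediate-1 | 2.7 | 5.7% | 0.6 | 0.3% |
| Intermediate-2 | 1.1 | 13.5% | 1.5 | 5.0% |
| High | 0.5 | 27.3% | 3.0 | 35% |

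The life-expectancy criterion pulls these figures down. Stopping for progression without death pushes k up. A k of 0 to 2 is plausible unless most of the remaining patients are high risk; k=4 is an extreme bound.

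**The case against.** A reader might infer that every death or progression in cycles 1 to 3 goes uncounted. The documents do not support that. A patient who worsens during those cycles, completes the third and is found progressed at C4D1 is evaluable and scored as Failure. The visit schedule also lists no bone marrow examination, so earlier progression would have to show in the per-cycle blood count, transfusion history or clinical review. That keeps k smaller than the number who progress biologically.

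A reader might also infer that the plan commits to an inflated response rate. It does not: no section promises a proportion or names its denominator, so the inflation is conditional on the Section 9.1 set being used. That objection stands as a condition. Section 9.1 is nevertheless the only text saying who is evaluable for response, so it is the natural denominator.

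The minimum exposure has a rationale. Section 1 says responses to azacitidine or decitabine usually take two or three cycles. Appendix 2 requires haematologic improvement to last at least 8 weeks and stable disease to be free of progression for more than 8 weeks. This supports keeping a three-cycle analysis. It does not support omitting patients whose outcome is already a defined Failure.

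Heavy early loss is unlikely. The 12-week criterion selects patients expected to survive the window. Inclusion criterion 6 admits patients with no indication for a hypomethylating agent or thought unable to tolerate one, while Section 1 calls these agents first-line for high-risk patients who can tolerate them. A cohort made up wholly of high-risk patients is therefore remote. No losses in seven is favourable but weak evidence: the exact 95% upper limit is 1 - 0.025^(1/7) = 41%.

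Finally, the methylation analysis keeps partial data because it is a longitudinal mixed model under a missing-at-random assumption. That is no precedent for scoring early stoppers as non-responders, and the point does not rest on it.

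**Conclusion.** The point holds, with modest impact. Section 9.1 leaves out patients who die, or stop for progression, before three cycles, although Appendix 2 scores them as Failure. If its set is the denominator and there is at least one responder, the proportion is inflated by 18/(18-k). With an assumed 4 responders and k of 1 or 2, the shift is 1.3 or 2.8 percentage points, small beside an interval of 6.4 to 47.6%. With no responders the proportion stays at zero. The formula assumes 18 treated patients and that those leaving early are non-responders.

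It would go too far to say the trial's response result is already biased: nothing has been lost among the first seven patients. This is a secondary endpoint with no stated target or test, and the primary methylation and toxicity analyses are untouched. The change is still worth making, because the effect runs one way and the remedy is cheap.

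**What to change.** In Section 9.1:

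- Make all patients who take at least one BRB dose the main denominator for best response.
- List deaths and progressions before three cycles as Failure.
- Count other early stoppers without a documented Appendix 2 response as non-responders, shown separately as not assessed rather than as Failure.
- Keep the three-cycle set as a supportive analysis.

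In Section 10, state the same denominator and report the proportion with an exact 95% confidence interval.

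The cost is two or three sentences in Section 9.1 and one in Section 10, with no new visits or samples. It is best done before the outcomes of the remaining 11 patients are known. The downside is that the reported proportion may be slightly lower and patients who stop for reasons unrelated to disease count as non-responders. Counting the not-assessed group this way is a choice of analysis that Appendix 2 does not dictate; the separate listing and the supportive set make its effect visible.
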